Objective and Rationale for Aims 1-2. We propose a cross-sectional study where we will compare PANESS and SICI measures in 20 children with NF1 with data already acquired at CCHMC with those 2 measures. Next, these 20 children will be treated with NAC as described below. PANESS and TMS measures will be repeated after 8 weeks of treatment. Clinical symptom ratings will be performed independently. Motor and TMS ratings and clinical ratings will be blinded to one another until analyses are completed at the end of

Version 9.0 MAR2020 Page 8 of 24

the study. At present, there are no clinical characteristics, neuropsychologic variables, phenotypic variants or biomarkers which can accurately predict treatment response of abnormal motor/learning behaviors in NF1 to NAC therapy. We will assess ADHD attention and hyperactive/impulsive symptoms with the DuPaul DSM-5 based clinical rating scales and predict an improved rating after treatment with NAC.

Screening Period: Screen candidates will be solicited from clinic referrals and from advertisements. If, after the screening visit, the candidate is determined eligible to participate, the candidate will then be entered into the baseline testing portion of the study.

Baseline Testing Period (Visit 0): Baseline testing may occur remotely, may coincide with the first study visit, or split among both options and will consist of clinical assessments and ADHD severity testing with evaluation by an independent rater blinded to study procedures as well as parent ratings of ADHD, assessment of anxiety, and depressive symptoms. Some participants may undergo a short, optional pretreatment, unsedated research MRI for structural and DTI. All participants will receive a full psychometric and neurological examination and be screened with a comprehensive assessment battery designed to guarantee that they meet inclusion/exclusion criteria for the study, that they are candidates to receive NAC being offered in the trial, and that a robust database is available regarding NF1 motor/learning behavior symptomatology, comorbid symptomatology, broader psychosocial function, neuropsychological function, academic performance, severity and impairment, and medical status. Per FDA Guidance for Industry: Suicidal Ideation and Behavior: Prospective Assessment of Occurrence in Clinical Trials, an assessment for suicide (Columbia Suicide Severity Rating Scale, C-SSRS) will be performed at every visit and monitoring visits or phone calls.

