Treatment Observation Period:

Phase I:

Study initiation will consist of motor PANESS and TMS measures (AIMS 1 and 2) and blood will be drawn for metabolomics profiles (AIM 3). Subjects will then return to the outpatient RASopathies clinic where they will be assigned to one of two treatment arms (NAC drug or placebo) of this study. Each subject will receive drug or placebo (visits 1 and 3) without feedback regarding treatment arm assignment to [name] until the end of the study. At each of these outpatient visits (visits 1 and 3) subjects will be assessed for vital signs, adverse events, pill counts and concomitant meds, and for motor/learning behaviors severity and improvement. At the final phase I and final study visits (visits 2 and 4, respectively), treatment outcomes will be rated by an independent rater as well as by the study physician ([name], or qualified designee) for motor/behavior improvement. A repeat longitudinal TMS study will occur at weeks 8 and 18 (at the end of phase I and phase II, respectively) while on a stable treatment dose of NAC or placebo (visits 2 and 4) by [name] within 8-10 hours following AM dosing. At end of the final phase I study visit (visit 2), subjects will undergo an 'interphase' for 1 week during which they will abstain from medication (drug or placebo). After interphase, subjects will enter phase two of this cross-over double-blind placebo controlled study and commence the alternative treatment arm.

Phase II:

In phase two, subjects will cross over to the opposite treatment arm (NAC drug or placebo) than they were assigned during phase one. All other details outlined in phase I will remain unchanged.

After both phases of the treatment observation period are complete, there will be a debriefing interview, in which children and their families will review both their performance during the trial and tolerability data (visit 5). A plan for follow-up care will be created by [name], or qualified designee, with referral for follow-up treatment. If needed, subjects will be given transition medication (atomoxetine or otherwise depending on effectiveness of study drug) until subject can establish appropriate care with a clinician.

Version 9.0 MAR2020 Page **9** of **24**

Emergency Study Extension

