	• PANESS	• PANESS		
	• C-SSRS	• C-SSRS		
	BRIEF (optional)	• BRIEF (optional)		
	- TMS rSICI/fSICI	- TMS rSICI/fSICI		

STUDY PROCEDURES:

Screening and Baseline Assessment (Visit 0):

All participants will receive a full psychometric and neurological examination at baseline, and be screened with a comprehensive assessment battery designed to guarantee that they meet inclusion/exclusion criteria for the study, that they are candidates to receive NAC being offered in the trial, and that a robust database is available regarding NF1 motor/learning behavior symptomatology, comorbid symptomatology, broader psychosocial function, neuropsychological function, academic performance, severity and impairment, and medical status. Some participants may undergo a short, optional pre-treatment, unsedated research MRI for structural and DTI. Baseline assessments may be collected at screening visit 1. Per FDA *Guidance for Industry: Suicidal Ideation and Behavior: Prospective Assessment of Occurrence in Clinical Trials*, an assessment for suicide (Columbia Suicide Severity Rating Scale, C-SSRS) will be performed at this visit.

Phase Initiation (Visits 1 and 3):

The second visit will be for baseline testing in a med-free state. All participants will receive a full physical and TMS testing (visits 1 and 3) as well as psychometric and neurological examination (at visit 3 only if baseline measurements were obtained at visit 1). At the end of visit 1 and 3, participants will be placed on 70 mg/kg/dose (max dose 900 mg) three times per day of NAC or placebo. Per FDA *Guidance for Industry:* Suicidal Ideation and Behavior: Prospective Assessment of Occurrence in Clinical Trials, an assessment for suicide (Columbia Suicide Severity Rating Scale, C-SSRS) will be performed at this visit.

Monthly Medication Monitoring and Safety Assessment (Phone calls,e-mails, and/or visits).

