The study physician ([name], or qualified designee) is responsible for evaluating the participant's clinical state each month, including both the progress of treatment and the occurrence of adverse events/tolerability problems. The study physician will interview child and family regarding level of clinical improvement and tolerability. They may obtain the participant's weight, pulse and blood pressure. Concomitant medications and adverse effects (e.g. SERS) will be reviewed (in person or via phone or email). [name] or designee will also question the subjects as to compliance with study medication. If needed [name] or designee may ask for the participant to bring in medication bottles to check pill count and can also check to see if the prescription has been filled/refilled at the reported times. At a monthly medication visit, the study physician or designee will: 1) do vitals; 2) evaluate adverse events both spontaneous and elicited, 3) and fill out medication log/assess compliance. Per FDA *Guidance for Industry: Suicidal Ideation and Behavior: Prospective Assessment of Occurrence in Clinical Trials*, an assessment for suicide (Columbia Suicide Severity Rating Scale, C-SSRS) will be performed.

Version 9.0 MAR2020 Page **14** of **24**

End of Phase I and End of Study visits (Visit 2, 4).

Participant will undergo a TMS evaluation at completion of 8 weeks of NAC or placebo. An independent rater will assess clinical outcome with the primary outcome measure (PANESS scale), the same rater that performed the baseline neuropsychometrics assessment (whenever possible). Participants will also meet with [name] and [name] to conduct the study closeout visit which consists of 1) vitals; 2) evaluate adverse events both spontaneous and elicited, 3) fill out medication log/assess compliance, 4) assess collateral symptoms of depression/anxiety which may have developed during the trial, 5) evaluate parent ratings, 6) write a progress note documenting the visit, 7) assign motor/learning behavior improvement, 8) meet with participant and family to review the child's performance during the trial to present a set of clinical recommendations for future care (not restricted to medication, and not for a specific medication). Per FDA Guidance for Industry: Suicidal Ideation and Behavior: Prospective Assessment of Occurrence in Clinical Trials, an assessment for suicide (Columbia Suicide Severity Rating Scale, C-SSRS) will be performed.

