Nervous system disorders	Headaches, Dyskinesias, Disturbances in initiating and maintain sleep,			
Psychiatric Disorders	Anxiety symptoms, decreased or increased physical activity levels, depressive symptom			
Gastrointestinal Disorders	Nausea, vomiting, constipation			

MRI (optional):

The MRI protocol will be comprised of imaging sequences providing high-resolution detail of brain tissue structure. A 3D T1-weighted volume will be acquired with ≤ 1 mm isotropic resolution and strong contrast between gray matter and white matter tissue. This image volume will be used for anatomic reference and may also serve to provide voxel-level volumetric assessments. A diffusion-tensor imaging (DTI) sequence (≤ 2 mm isotropic resolution) will follow, which is directionally sensitive to the rate of water diffusion in brain tissue. This sequence will measure diffusion rates in 32 or more directions to allow voxel-wise determination of diffusion anisotropy. This is especially useful in white matter, where restricted diffusion of axonal structures leads to a high degree of anisotropy that reflects tissue integrity.

The T1-weighted image will be processed using one of the commonly available software packages for MRI, including FSL (http://www.fmrib.ox.ac.uk/fsl/) or SPM (Wellcome Trust Centre for Neuroimaging). Processing will include segmentation into gray matter, white matter, and cerebrospinal fluid tissue types and normalized by transformation into a common spatial template (MNI). DTI volumes will have been aligned to each other and with the T1 anatomic image and normalized to the same template space before processing in FSL to extract mean diffusivity (MD) and fractional anisotropy (FA) on a voxel-wise basis. In healthy white matter, diffusion will be greatest along axonal fibers and FA describes the degree to which axial diffusion exceeds transverse diffusion. Images may be processed in other ways to extract additional structural information. The T1 segmentations may be analyzed as tissue probability maps for voxel-based morphometry. The DTI data may allow axonal fiber tractography to ascertain structural connectivity between brain regions.

Since all images will have been normalized to the same space, voxel-wise comparisons across subjects will be possible. Our primary imaging outcomes in white matter will be voxel-wise comparison of FA

Version 9.0 MAR2020 Page **17** of **24**

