between NAC and Placebo groups and regional correlation between FA and neuropsychometric outcomes. Other imaging measures, some outlined above, may also undergo these comparisons.

Clinical Scales:

ADHD – Dupaul ADHD-RS, parent form.

This 18 question scale is based on the DSM-5 and is widely used in clinical trials and routine care.

Behavioral Rating Inventory of Executive Function (BRIEF)

The Behavioral Rating Inventory of Executive Function (BRIEF) is a parent-reported symptom rating form that is used regularly in NF1 research. This assessment measures executive function behaviors at home and at school for children and adolescents (age 5–18). This scale would give a sense of if any changes are occurring in real-world executive function.

Pediatric Anxiety Rating Scale (PARS) [21]

The PARS is a clinician rated scale that is completed following interview with the parent and child. The PARS has two sections, a symptom checklist and severity items, each of which is linked to the past week. We chose PARS over several possible self-report scales because young children may not be able to complete a self-report scale.

Children's Depression Rating Scale (CDRS) [22]

The CDRS is a clinician-completed scale that rates presence and severity of depressive symptoms, based on interviews with the parent and child separately. There are 17 behavior items of affective state, rated dimensionally normed for children 6-12 years.

Cognitive Function.

Each child will be administered a psychological screening battery by trained research assistants under the supervision of a licensed psychologist, to assist in evaluation of inclusion and exclusion criteria, and to identify co-morbid disorders (e.g. learning disorder). Assessment of cognitive function will be used to assess suitability for the study and to describe the sample. Within the constraints of limited time and resources, we have selected the following tests to evaluate cognitive functioning and learning problems. *KBIT-2 (Kaufman Breif Intelligence Test, Second Edition)* [23] validated for use in 6-12 year olds, consisting of 2 subtests (Vocabulary, Similarities) assessing verbal IQ and 2 subtests (Block Design, Matrix Reasoning) assessing performance IQ will be used with an administration time of 30 minutes which will provide an estimate for performance IQ, verbal IQ and full scale IQ.

PANESS scale:

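### The NAC-versus-placebo comparison of fractional anisotropy (FA) cannot show a treatment effect, because MRI is scheduled only before the first dose; an unnamed one-hour scan at later visits needs reconciling

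*Combined protocol and SAP*

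**What the plan says.** The MRI (optional) section under Study Procedures states: "Our primary imaging outcomes in white matter will be voxel-wise comparison of FA", and the sentence continues "between NAC and Placebo groups and regional correlation between FA and neuropsychometric outcomes". That gives two primary imaging outcomes: a treatment comparison of FA, and a correlation of FA with test scores. The next sentence extends the plan: "Other imaging measures, some outlined above, may also undergo these comparisons".

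The timing of MRI is given in four places:

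- Study Design, Baseline Testing Period (Visit 0): "Some participants may undergo a short, optional pretreatment, unsedated research MRI for structural and DTI".
- Study Procedures, Screening and Baseline Assessment (Visit 0): "Some participants may undergo a short, optional pre-treatment, unsedated research MRI for structural and DTI".
- Table 2: MRI appears in the Visit 0 screening column and in no other.
- Table 3: the MRI row has one mark, in the Visit 0 column (week -1). The TMS, PANESS and metabolomics rows have four marks each.

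The Table 3 footnote leaves it to the study doctor to decide who is offered the scan.

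One further text bears on timing. The visit description before Table 2, in the informed consent section, covers the on-site visits in each phase, after a screening and baseline that happen once. It lists about 120 minutes of assessment, a 90-minute TMS session and 60 minutes of scanning, for a total of 5 to 6 hours. It does not say what kind of scan this is.

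**The concern.** A treatment comparison needs an outcome measured after treatment has begun. By the schedule, FA is measured only before it. Each child takes both NAC and placebo in turn, so before the first dose the only NAC and placebo groups are the children who will receive one or the other first. Comparing their FA describes how alike the two sequence groups were at entry.

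The risk is misreading. A voxel that differs by chance or through baseline imbalance would appear under a NAC-versus-placebo label and could be taken as an effect on white matter. The scanned children are also a subset of unstated size chosen by the study doctor, so imbalance is plausible. The sentence on other imaging measures carries the same problem to those measures.

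**Working it through.** The plan gives no effect size, power or number of children for FA, so there is no figure of its own to reproduce. The main check sets the schedule against the outcome.

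**1. Order of scan and dose.** MRI is at week -1 in Table 3. Baseline testing may coincide with the first study visit, but drug or placebo starts only at the end of Visit 1 (Phase Initiation). A scan moved to Visit 1 as part of baseline testing is therefore still before dosing.

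**2. What the contrast estimates.** With FA measured before dosing, and sequence assigned independently of baseline FA (assumption):

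E[FA | NAC first] - E[FA | placebo first] = 0 at every voxel.

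A test at the 0.05 level in section 9 (Statistical Analysis) therefore rejects 5% of the time per voxel, whatever the true effect of NAC. Its power equals its type I error rate. If the assumption fails, the contrast shows baseline imbalance, which is still not a treatment effect.

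**3. Simulation check.** One FA value per child, 20 children, 10 per sequence, two-sided t test at 0.05, 20,000 runs for each effect size. The last column shows, for contrast, a paired test on scans at the end of both phases, assuming a within-child correlation of 0.7 and no carryover or period effect.

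| True NAC effect (SD) | Pre-dose scan: mean estimate (SD) | Pre-dose scan: rejection | End-of-phase scans: rejection |
|---|---|---|---|
| 0 | 0.001 | 4.7% | 5.2% |
| 0.5 | 0.002 | 4.8% | 78.1% |
| 1.0 | 0.005 | 4.9% | 100% |
| 2.0 | 0.001 | 4.8% | 100% |

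The pre-dose columns do not respond to the true effect. The last column is not a power estimate for this trial: the number scanned, the correlation and any voxel-wise correction are not given.

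**4. Across the map.** With m independent null tests, the chance of at least one false positive is 1 - 0.95^m:

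- m = 10: 1 - 0.5987 = 0.401
- m = 100: 1 - 0.0059 = 0.994

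These m are illustrative. Positive correlation between voxels lowers the figures, down to 0.05 if all voxels moved together. The Metabolomic Analyses section states Bonferroni and FDR correction; the MRI section states none.

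**5. The unnamed scan.** The itemised times sum to 120 + 90 + 60 = 270 minutes, or 4.5 hours, against a stated 5 to 6 hours, so the total does not settle what the scan is. It could be MRI. It could be magnetoencephalography (MEG), which the TMS section says will be collected but which neither table schedules. It could also be leftover text. Both baseline sections call the MRI short, which sits uneasily with an hour of scanning.

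**The case against.** The strongest reply is that the hour of scanning belongs to the phase visits, so on-treatment MRI may have been intended and merely left out of the tables. The tables are not complete: MEG is in neither, and the EKG mentioned under Contingency Option 2 is in neither. The two baseline sections say what may happen at Visit 0; they do not rule out a later scan.

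This stands in part. Confidence is high that the texts conflict, but only moderate that MRI was meant to be pre-treatment only. If on-treatment MRI was intended, both tables and both pre-treatment statements need correcting, so the document is wrong under either reading.

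It is also fair that silence at later visits proves little. The text says "A repeat longitudinal TMS study will occur at weeks 8 and 18" and "Participant will undergo a TMS evaluation at completion of 8 weeks of NAC or placebo" without mentioning MRI, but those descriptions also omit the metabolomics draw that both tables place at the same visits. The conclusion therefore rests on the four places that schedule MRI by name.

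Two further points are accepted. Multiplicity is a separate matter, since a pre-dose contrast would be uninformative even with perfect correction. And the stakes are small: the study is framed as preliminary, and MRI is optional.

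**Conclusion.** The concern holds. As scheduled, the FA comparison of NAC with placebo carries no information on treatment. Its expected value is zero and its false-positive rate is 5% per voxel, assuming sequence is unrelated to baseline FA; without that assumption it measures baseline imbalance. The same applies to any other imaging measure taken only at that time. The correlation of FA with neuropsychometric scores is unaffected and can be estimated from pre-treatment scans.

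The error is clear but limited in reach. No conclusion on PANESS, the ADHD rating scale, TMS or metabolomics depends on it. It should be corrected because a named primary imaging outcome currently has no scheduled data that could answer it.

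**What to change.** 1. **Establish which scans were planned or acquired.** In the visit description before Table 2, name the scan, its length and its visits, and make Tables 2 and 3 and the MEG paragraph agree with it.

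2. **If MRI is pre-treatment only,** delete the FA treatment comparison and limit the following sentence on other imaging measures to correlation analyses. Possible text: *The imaging outcome is the association of regional FA before treatment with neuropsychometric scores (baseline scores; later scores or change as exploratory prediction), reported descriptively with 95% confidence intervals for the children scanned.* If any of these associations is tested formally, state how multiplicity is handled.

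3. **If on-treatment MRI exists,** list it by visit in Tables 2 and 3, correct the pre-treatment wording in both baseline sections, describe the contrast as within child and not between groups, and state the voxel-wise multiplicity control.

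The cost is one check of the scan records or plans, then about three sentences in the first case, or table entries and some rewording in the second. No new data are needed. In the first case the trial gives up an imaging treatment comparison that its scheduled data could not support.
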